7.1.7. Additional Analysis of Adverse Events

Categories of AEs of special interest will be summarized (number and percentage) by treatment group. Table 7-1 presents the method of selecting preferred terms for each specified AE category.

Table 7-1. Methods in Selecting Preferred Terms for Specified AE of Interest Categories

AE of Interest Category	Methods in Selecting Preferred Terms
Cardiac failure	Broad Standardized MedDRA Query (SMQ) Cardiac Failure
Acute Renal Failure	Narrow SMQ Acute Renal Failure
COVID-19	Narrow SMQ COVID-19

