8.6. Safety Analysis

Safety will be assessed during the study through the reporting of AEs, and by clinical laboratory tests and vital sign assessments at various time points during the study. Concomitant medication usage will also be assessed throughout the study.

All safety data collected on or after the date that SEL or PTM was first dispensed up to the date of last dose of SEL or PTM plus 30 days, including data collected during the Run-in period, will be summarized by treatment group (according to the study drug received).

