3. GENERAL CONSIDERATIONS FOR DATA ANALYSES

Analysis results will be presented using descriptive statistics. For categorical variables, the number and percentage of subjects in each category will be presented; for continuous variables, the number of subjects (n), mean, standard deviation (SD), median, first quartile (Q1), third quartile (Q3), minimum, and maximum will be presented.

By-subject listings will be presented for all subjects in the Safety Analysis Set and sorted by subject ID number, visit date, and time (if applicable). Data collected on log forms, such as AEs, will be presented in chronological order within the subject. For randomized subjects, the treatment group to which subjects were randomized will be used in the listings. Age, sex at birth, race, and ethnicity will be included in the listings, as space permits.

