3.1.5. Safety Analysis Set

The Safety Analysis Set includes all subjects who took at least 1 dose of Run-in SEL. This is the primary analysis set for safety analyses.

CCI

[REDACTED]

[REDACTED]

[REDACTED]

[REDACTED]

CCI

[REDACTED]

[REDACTED]

[REDACTED]

CCI

[REDACTED]

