3.2. Subject Grouping

For analyses based on the Full Analysis Set, subjects will be grouped according to the treatment to which they were randomized. For analyses based on the PP Analysis Set, subjects will be grouped according to the actual treatment received in the Randomization phase. For exposure-adjusted incidence rate (EAIR) analyses based on the Safety Analysis Set, subjects and events will be grouped according to exposure (SEL or placebo). Please refer to Section 7 for details on EAIR analyses. The actual treatment received will differ from the randomized treatment only when their actual treatment differs from randomized treatment for the entire treatment duration.

For the PK Analysis Set, subjects will be grouped according to the actual treatment they received.

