7. SAFETY ANALYSES

Unless otherwise specified, summaries of safety data will be provided for the Safety Analysis Set and will include data collected up to the last dose of study drug plus 30 days.

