7.1.5. Treatment-Emergent Adverse Events

7.1.5.1. Definition of Treatment-Emergent Adverse Events

Treatment-emergent adverse events (TEAEs) are defined as follows for SEL and placebo exposures, respectively.

- SEL exposure: TEAEs are defined as 1 or both of the following:
 - Any AEs with an onset date on or after the Run-in SEL start date and no later than 30 days after permanent discontinuation of SEL
 - Any AEs leading to premature discontinuation of SEL

- Placebo exposure: TEAEs are defined as any AEs with an onset date on or after Study Day 31 (30 days after the Randomized placebo start date) and no later than 30 days after permanent discontinuation of Randomized placebo

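### The special-interest adverse event table (SAP 7.1.7) is by treatment group, so run-in SEL events in placebo-randomized subjects most likely count as placebo, and never-randomized subjects have no stated column

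*SAP*

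**What the plan says.** - **The special-interest table.** SAP 7.1.7: "Categories of AEs of special interest will be summarized (number and percentage) by treatment group". Table 7-1 lists three categories: cardiac failure (broad SMQ), acute renal failure (narrow SMQ) and COVID-19 (narrow SMQ). The section names no onset window and no analysis set.
- **Population and window.** SAP 3.1.5: "The Safety Analysis Set includes all subjects who took at least 1 dose of Run-in SEL". SAP 7 makes this set the default for safety summaries, which "will include data collected up to the last dose of study drug plus 30 days". That is an upper limit only.
- **Grouping.** SAP 3.2: "For exposure-adjusted incidence rate (EAIR) analyses based on the Safety Analysis Set, subjects and events will be grouped according to exposure (SEL or placebo)". It adds: "The actual treatment received will differ from the randomized treatment only when their actual treatment differs from randomized treatment for the entire treatment duration". SAP 3, on listings: "For randomized subjects, the treatment group to which subjects were randomized will be used in the listings".
- **What counts as a SEL event.** SAP 7.1.5.1 includes, for SEL exposure: "Any AEs with an onset date on or after the Run-in SEL start date and no later than 30 days after permanent discontinuation of SEL". For placebo exposure, counting starts on Study Day 31. SAP 7.1.6 summarises the other adverse event tables by exposure type, with exposure-adjusted incidence rates (EAIRs).
- **Protocol.** Section 8.6 says that safety data, "including data collected during the Run-in period, will be summarized by treatment group (according to the study drug received)". SAP 7.7 reports no departure from the protocol's safety analyses.

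**The concern.** Both arms spend the run-in on SEL. A renal or cardiac failure event in that period is a SEL event under SAP 7.1.5.1 whatever arm the subject later joins. A table by treatment group can put the same event under placebo, so two tables in one report would attribute it differently.

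Subjects who stop drug permanently in the run-in, whose eGFR falls below 15, or who have an ongoing significant illness are not randomized (Protocol 4.4). Those with a serious renal or cardiac event on SEL are therefore among the likelier ones to lack a column.

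Apart from COVID-19, these are the only categories that SAP 7.1.7 singles out. Both had a higher count on SEL 18 mg than on placebo in Phase 2 (Protocol Table 1-4). If SEL does raise the risk, SEL events in the placebo column pull the displayed ratio toward 1.

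**Working it through.** The documents give no figure for this table, so there is nothing to reproduce. The check has three parts.

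**1. Where a run-in event falls.** Take a placebo-randomized subject with acute renal failure on run-in SEL.
- The subject is in the Safety Analysis Set, which begins with run-in SEL (SAP 3.1.5).
- The event is inside the window, which has no lower limit (SAP 7). Protocol 8.6 expressly includes run-in data.
- Exposure grouping is given for EAIR analyses only (SAP 3.2). A number-and-percentage table is not one.
- Run-in SEL does not make actual treatment differ for the entire duration, so the subject stays in the placebo group (SAP 3.2).
- Result: placebo column in 7.1.7, SEL exposure in 7.1.6.

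For a subject never randomized, 7.1.7 names no column. SAP 4.3 and 7.5.1 to 7.5.3 add randomization status to their summaries; 7.1.7 does not.

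**2. Illustrative size.** Inputs:
- Phase 2 risks over 48 weeks (Protocol Table 1-4). Acute kidney injury (AKI): 6/83 = 7.23% on SEL 18 mg, 2/85 = 2.35% on placebo. Congestive cardiac failure: 5/83 = 6.02% and 2/85 = 2.35%.
- Run-in SEL lasts R = 21 + 7 = 28 to 28 + 14 = 42 days (visit windows, Protocol Appendix 2).
- Randomized follow-up T is 336 days (48 weeks, the minimum) or 588 days (84 weeks, the SAP's primary horizon).
- Planned size is 150 per arm.
- Assumptions: constant hazards, the run-in hazard equal to the later SEL hazard, and everyone randomized and followed.

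Formulas: daily hazard h = −ln(1 − p)/336; run-in risk q = 1 − exp(−h_SEL × R); each column then shows 1 − (1 − q)(1 − p_arm).

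AKI: h_SEL = 0.0002233 and h_placebo = 0.0000709 per day, a hazard ratio of 3.15. So q = 0.62% at 28 days and 0.93% at 42 days.

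| | T | Randomized phase only | With run-in, R = 28 | With run-in, R = 42 |
|---|---|---|---|---|
| AKI, SEL vs placebo | 48 wk | 7.2% vs 2.4%, ratio 3.07 | 7.8% vs 3.0%, ratio 2.64 | 8.1% vs 3.3%, ratio 2.48 |
| AKI | 84 wk | ratio 3.02 | ratio 2.75 | ratio 2.64 |
| Cardiac failure | 48 wk | 6.0% vs 2.4%, ratio 2.56 | ratio 2.28 | ratio 2.17 |
| Cardiac failure | 84 wk | ratio 2.52 | ratio 2.35 | ratio 2.28 |

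At 48 weeks, expected placebo-column subjects with AKI rise from 150 × 0.0235 = 3.5 to between 4.4 and 4.9.

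The two columns differ by (1 − q)(p_SEL − p_placebo), so the risk difference is only multiplied by 1 − q. For AKI at 48 weeks it goes from 4.88 points to 4.85 (28 days) or 4.83 (42 days).

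**3. Whether the EAIR definitions can simply be reused.** Under SAP 7.1.5.1 the SEL numerator runs to 30 days after SEL stops; under 7.1.6.1 the SEL denominator stops at the last dose. The placebo numerator starts on Day 31 but its denominator starts on Day 1. With equal arms and no true effect, the SEL numerator covers (R + T + 30) + (R + 30) days per pair of subjects against 2R + T in the denominator. The placebo numerator covers T days against T. For R = 28 and T = 336 the rate ratio is close to 452/392 = 1.15. For R = 42 and T = 588 it is close to 732/672 = 1.09. The exact calculation, with a background risk of 5% per 48 weeks (assumption), gives 1.09 to 1.15 over the four combinations.

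**The case against.** **Placement is inferred.** SAP 7.1.7 does not define treatment group or an onset window, and the words in Protocol 8.6 about the drug received allow another reading. This stands, and it is why the point speaks of the likeliest reading. It does not remove the need for a change: 7.1.7 does not say how one subject's events would be divided between two drugs.

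**The events are shown correctly elsewhere.** SAP 7.1.6.3 gives EAIRs by exposure type for each preferred term, SAP 7.1.6.1 counts never-randomized subjects' run-in SEL exposure, and listings cover all enrolled subjects. This stands and limits the weight of the point. It does not replace the SMQ table, because one subject may have several preferred terms, so those counts cannot be added to give the number of subjects in a category.

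**The Phase 2 contrast is weak.** The counts are 6/83 against 2/85 and 5/83 against 2/85 (Fisher p = 0.17 and 0.27), for single preferred terms rather than SMQs. Serious AKI went the other way, 1.2% on SEL 18 mg against 2.4% on placebo (Protocol Table 1-5). This stands; the ratios only illustrate the mechanism.

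**A stronger reading is tempting.** SEL lowers eGFR acutely, by about 10% at Week 4 (Protocol 7.5.5), so a reader might infer that the AKI excess also falls mainly in the shared run-in. If half of it did, the risk difference would halve from 4.88 to 2.44 points, and the ratio would fall to about 7.23/(2.35 + 2.44) = 1.5. The documents do not support that inference. They give no AKI or cardiac failure onset times. Protocol 1.2.3.2.3 attributes the eGFR fall in part to creatinine transport, and Protocol 1.2.3.1 describes the fall in measured GFR as rapidly reversible without evidence of nephrotoxicity. Run-in creatinine and eGFR are mostly withheld from sites (Protocol 5.1, 6.4.12), which could reduce AKI reporting in that period.

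**Conclusion.** The point holds as an inconsistency of moderate weight. On the likeliest reading, SAP 7.1.7 credits run-in SEL events to placebo for subjects later randomized to placebo, and it leaves never-randomized subjects without a column. That conflicts with SAP 7.1.5.1 and 7.1.6 and with Protocol 8.6.

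Under constant hazards the AKI ratio shown falls by about 9% to 19% and the cardiac failure ratio by about 7% to 15%. These figures also assume that SEL truly raises the risk. With a higher early hazard the dilution would be larger, but the documents provide nothing from which to size it.

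A reader might go further and conclude that the safety signal is lost, or that the arms are unbalanced in follow-up because SEL subjects carry extra run-in time. Neither follows. The preferred-term analyses retain the signal, both arms have the same planned run-in, and no test or decision rule depends on this table.

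**What to change.** Amend SAP 7.1.7 in one of two ways.

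- **(a) By exposure type.** Report each SMQ category as number of subjects and EAIR under SEL or placebo exposure, with never-randomized subjects under SEL. Align the numerator and denominator windows first; otherwise the table favours placebo by about 9% to 15% when there is no effect. Plain percentages by exposure type would not do, because exposure times are unequal.
- **(b) By phase.** Report events with onset after randomization by randomized arm, and add a separate run-in SEL summary that includes subjects never randomized.

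Either way, state the onset window and the column for never-randomized subjects. No new data are needed. The cost is a short wording change and a little extra programming, mainly to align the windows under (a).

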7.2. Laboratory Evaluations

Central laboratory data collected during the study will be analyzed and summarized using both quantitative and qualitative methods. Summaries of central laboratory data will be provided for the Safety Analysis Set and will include data collected up to the last dose of study drug plus 30 days for subjects who have permanently discontinued study drug. The analysis will be based on values reported in conventional units. When values are below the LOQ, they will be listed as such, and the closest imputed value will be used for the purpose of calculating summary statistics as specified in Section 3.7. Hemolyzed test results will not be included in the analysis, but they will be listed in by-subject laboratory listings.

A by-subject listing for central laboratory test results will be provided by subject ID number and visit in chronological order for hematology, serum chemistry, and urinalysis separately. For central laboratory data, values falling outside of the relevant reference range and/or having a severity grade of 1 or higher on the CTCAE severity grade will be flagged in the data listings, as appropriate.

A by-subject listing for local laboratory test results will also be provided by subject ID number and collection date in chronological order. Test values and corresponding reference ranges reported by the local laboratories will be presented.

No formal statistical testing is planned.

7.2.1. Summaries of Numeric Laboratory Results

Descriptive statistics will be provided by treatment group for each central laboratory test specified in the study protocol as follows:

- Baseline values
- Values at each postbaseline visit
- Change from Baseline at each postbaseline visit

A Baseline laboratory value will be defined as the last nonmissing measurement obtained on or prior to the date/time of first dose of Run-in SEL, with the exception that Baseline laboratory values for serum creatinine, serum cystatin C, eGFR_{cr}, eGFR_{cys}, urine albumin, urine creatinine and UACR will be defined as the average values of Visit A and Visit B measurements. Change from Baseline to a postbaseline visit will be defined as the visit value minus the Baseline value. The mean, median, Q1, Q3, minimum, and maximum values will be displayed to the reported number of digits; SD values will be displayed to the reported number of digits plus 1.

Median (Q1, Q3) of the change from Baseline values for white blood cells, neutrophils, lymphocytes, hemoglobin, platelet count, serum creatinine, eGFR_{cr}, serum cystatin C, eGFR_{cys}, UACR, total bilirubin, aspartate aminotransferase (AST), alanine aminotransferase (ALT) and alkaline phosphatase (ALP) will be plotted using a line plot by randomization status, treatment group and visit.

In the case of multiple values in an analysis window, data will be selected for analysis as described in Section 3.8.3.

7.2.2. Graded Laboratory Values

The modified CTCAE v5.0 criteria as specified in the protocol will be used for assigning toxicity grades (0 to 4) to central laboratory results for analysis.

Severity grading for serum creatinine will be defined with the following criteria for reporting purposes. Any serum creatinine within the normal range should be grade 0 regardless of the criteria specified.

Grade 1	Grade 2	Grade 3	Grade 4
1.25 to < 1.5 x Baseline	1.5 to < 1.75 x Baseline	1.75 to ≤ 3 x Baseline	>3 x Baseline

Severity grading for serum cystatin C will be defined with the following criteria for reporting purposes. Any serum cystatin C within the normal range should be grade 0 regardless of the criteria specified.

Grade 1	Grade 2	Grade 3	Grade 4
1.25 to < 1.5 x Baseline	1.5 to < 1.75 x Baseline	1.75 to \leq 3 x Baseline	>3 x Baseline

Grade 0 includes all values that do not meet the criteria for an abnormality of at least Grade 1. For laboratory tests with criteria for both increased and decreased levels, analyses for each direction (ie, increased, decreased) will be presented separately.

7.2.2.1. Treatment-Emergent Laboratory Abnormalities

Treatment-emergent laboratory abnormalities are defined as follows for SEL and placebo exposures, respectively. Treatment-emergent laboratory abnormalities will only be evaluated for central laboratory testing results.

- SEL exposure: values that increase at least 1 toxicity grade from Baseline at any time point after the first dosing date of Run-in SEL, up to and including the date of last dose of SEL plus 30 days.
- Placebo exposure: values that increase at least 1 toxicity grade from Baseline at any time point on or after Study Day 31, up to and including the date of last dose of Randomized placebo plus 30 days.

Baseline is defined as the last nonmissing value prior to the first dose of Run-in SEL.

If the relevant Baseline laboratory value is missing, any abnormality of at least Grade 1 observed within the time frame specified above will be considered treatment emergent.

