7.1.6. Summaries of Adverse Events and Deaths

Exposure-adjusted treatment-emergent AE incidence rates will be summarized based on the Safety Analysis Set, by exposure type (SEL or placebo) and overall. SEL exposure includes Run-in SEL exposure and Randomized SEL exposure.

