7.2.2.2. Treatment-Emergent Marked Laboratory Abnormalities

Treatment-emergent marked laboratory abnormalities are defined as follows for SEL and placebo exposures, respectively. Treatment-emergent marked laboratory abnormalities will only be evaluated for central laboratory testing results.

- SEL exposure: values that increase at least 2 toxicity grades from Baseline at any time point after the first dosing date of Run-in SEL, up to and including the date of last dose of SEL plus 30 days.
- Placebo exposure: values that increase at least 2 toxicity grades from Baseline at any time point on or after Study Day 31, up to and including the date of last dose of Randomized placebo plus 30 days.

Baseline is defined as the last nonmissing value prior to the first dose of Run-in SEL.

If the relevant Baseline laboratory value is missing, any Grade 2, 3 or 4 values observed within the time frame specified above will be considered treatment emergent.

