7.2.3. Liver-related Laboratory Evaluations

Liver-related abnormalities after initial study drug dosing will be examined and summarized using the number and EAIR of subjects who were reported to have the following central laboratory test values for postbaseline measurements:

- AST: (a) > 3 times of the upper limit of reference range (ULN); (b) > 5 x ULN; (c) > 10 x ULN; (d) > 20 x ULN
- ALT: (a) > 3 x ULN; (b) > 5 x ULN; (c) > 10 x ULN; (d) > 20 x ULN
- AST or ALT: (a) > 3 x ULN; (b) > 5 x ULN; (c) > 10 x ULN; (d) > 20 x ULN
- Total bilirubin: (a) > 1 x ULN; (b) > 2 x ULN
- ALP: > 1.5 x ULN
- AST or ALT > 3 x ULN and (a) total bilirubin > 1.5 x ULN; (b) total bilirubin > 2 x ULN; (c) total bilirubin > 2 x ULN and ALP < 2 x ULN

The summary will include data for the following exposure periods for SEL and placebo exposures, respectively:

- SEL exposure: at any time point after the first dosing date of Run-in SEL, up to and including the date of last dose of SEL plus 30 days.
- Placebo exposure: at any time point on or after Study Day 31, up to and including the date of last dose of Randomized placebo plus 30 days.

For individual laboratory tests, subjects will be counted once based on the most severe values in corresponding period. For both the composite endpoint of AST or ALT and total bilirubin, subjects will be counted once when the criteria are met at the same postbaseline visit date. A listing of subjects who met at least 1 of the above criteria will be provided.

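### Placebo-emergent laboratory abnormalities need not be new, so one that arose on run-in SEL and persists past Study Day 31 is counted under both exposures

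*SAP*

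**What the plan says.** SAP 7.2.2.1 defines laboratory emergence by value and calendar window.

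- **SEL window:** "SEL exposure: values that increase at least 1 toxicity grade from Baseline at any time point after the first dosing date of Run-in SEL". It closes 30 days after the final SEL dose.
- **Placebo window:** "Placebo exposure: values that increase at least 1 toxicity grade from Baseline at any time point on or after Study Day 31". It closes 30 days after the final randomized placebo dose.
- **Reference for both:** "Baseline is defined as the last nonmissing value prior to the first dose of Run-in SEL".

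Section 7.2.2.2 repeats this for marked abnormalities: "Placebo exposure: values that increase at least 2 toxicity grades from Baseline at any time point on or after Study Day 31". Section 7.2.3 tabulates fixed multiples of the upper limit of normal, with no comparison to Baseline, over the same window: "Placebo exposure: at any time point on or after Study Day 31".

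The run-in SEL of subjects later randomized to placebo belongs to the SEL column, since "SEL exposure includes Run-in SEL exposure and Randomized SEL exposure" (SAP 7.1.6). Under SAP 7.2.2.3, laboratory rates are computed as for adverse events. SAP 7.1.6.3 counts a subject once within each exposure type, but nothing prevents the same subject from being counted in both.

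Adverse events follow a different rule. For placebo, "TEAEs are defined as any AEs with an onset date on or after Study Day 31" (SAP 7.1.5.1). An adverse event that began on SEL and is still ongoing is therefore not a placebo event.

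**The concern.** Every subject randomized to placebo has taken SEL for at least 4 weeks since the Baseline value. A grade above that Baseline at Week 8 may have arisen on SEL, but the laboratory rule takes no account of when it arose. The adverse-event rule does, so the same safety section attributes carried-over findings in two different ways.

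What is at stake is the SEL/placebo comparison of laboratory abnormalities, reported as numbers and exposure-adjusted incidence rates (EAIRs). Carry-over adds to the placebo numerator. If SEL causes an abnormality that lasts more than about a month off drug, part of that signal moves into the comparator and the ratio shrinks.

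**Working it through.** The plan gives no figure for this, so there is none to reproduce. The check applies the rule to a case and then sizes it under stated assumptions.

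**1. Window arithmetic.** If the last run-in SEL dose is the day before Study Day 1, the SEL window ends on Day 30 and the placebo window opens on Day 31. If run-in SEL is taken on Day 1, which SAP 3.1.4 allows for, the SEL window ends on Day 31 and that day falls in both. Week 4 is nominally Day 29 ± 5, that is Days 24 to 34, so a late Week 4 draw is already in the placebo window. From Week 8 (Day 57) every scheduled draw is.

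**2. One subject.** Randomized to placebo; Grade 0 before SEL; Grade 1 at Visit C, Day 1 and Weeks 4, 8 and 12. Under the SAP rule the subject counts under SEL (Visit C) and under placebo (Week 8). If a placebo event must be new since the last value before Day 31, the subject counts under SEL only.

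**3. Added placebo rate.** Added EAIR per 100 patient-years = 100 × p × q / T. Here p is the share of placebo subjects with an abnormality that emerged in the SEL window, q is the share of those still qualifying on or after Day 31, and T is patient-years per subject. All three are assumed. T = 48/52.18 = 0.92 or 84/52.18 = 1.61.

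| p | q | T = 0.92 | T = 1.61 |
|---|---|---|---|
| 2% | 25% | 0.5 | 0.3 |
| 5% | 50% | 2.7 | 1.6 |
| 10% | 50% | 5.4 | 3.1 |
| 20% | 100% | 21.7 | 12.4 |

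Take 150 placebo subjects, p = 10%, q = 50%, and suppose 10% of the rest have a truly new abnormality. Carried over: 150 × 0.05 = 7.5. New: 150 × 0.95 × 0.10 = 14.25. The SAP rule counts 21.75 subjects, or 15.8 per 100 patient-years at T = 0.92. The newness rule counts 14.25, or 10.3. The ratio is 21.75/14.25 = 1.53.

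**4. Share of the placebo count.** A two-state simulation used 200,000 subjects per setting and no dropout. Onset was 0.1-0.8 per year and mean persistence 0.25-3 years. Draws were at weeks 3.5, 5 and 9 after SEL start, then at Weeks 8 to 72 after Day 1. The share of the placebo count with no new onset after the last draw before Day 31 was about 8-16% with no SEL effect, and roughly 13-30% if SEL triples onset and its abnormalities last as long off drug as background ones. At a fixed SEL rate and fixed person-time, a carry-over share c multiplies the SEL/placebo ratio by 1 − c: 0.84-0.92 and 0.70-0.87 respectively.

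**5. Person-time.** SAP 7.1.6.1 stops SEL exposure at the last SEL dose, while SEL events count for 30 days more. The visit windows put run-in SEL at 28 to 42 days (21-28 plus 7-14). At the midpoint of 35 days, a placebo-randomized subject is at risk for 35 + 30 = 65 days over a 35-day denominator. For placebo, exposure runs from Day 1 to last dose (day L), which is L days; the counting window, Day 31 to L + 30, is also L days. The mismatch in length is therefore on the SEL side.

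SEL/placebo EAIR ratios in the simulation with **no** SEL effect:

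| Rule | SAP person-time | Window-matched person-time |
|---|---|---|
| Current | about 0.99-1.10 | about 0.89-0.99 |
| Newness required | about 1.12-1.24 | about 1.01-1.12 |

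**The case against.** The strongest reply has four parts.

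**SEL effects may be gone by Day 31.** Protocol 1.2.3.1 reports that the acute GFR and eGFR decreases had reversed by Day 56, after a 28-day washout, and Protocol 1.2.2.3 describes the nonclinical findings as generally reversible. A reader might infer that the rule hides the known creatinine effect, but the documents do not support that. Grade 1 creatinine in SAP 7.2.2 starts at 1.25 × Baseline, an eGFR fall of 1 − 1.25^(−1.209) = 23.6%. Protocol 7.5.5 says about a quarter of subjects had an acute fall of 19% or more, and the median was 10%. This part stands: the lag is a partial washout, and quickly reversible effects add little. It does not cover slower effects.

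**Much of the carry-over is background.** With onset 0.3 per year, 3-year persistence and a threefold SEL effect, placebo reads 38% under the current rule and 29% if newness is required. With no SEL effect the current rule already reads about 35%, so SEL itself adds about 3 points. One might infer that dilution always grows with the SEL effect. It does so only for effects that persist off drug; with an assumed 2-week mean off-drug recovery the 38% falls back to 35%.

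**A newness rule alone creates a bias against SEL.** This is correct (step 5), and the fix has to deal with it.

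**Other outputs show carry-over.** Summaries by visit and treatment group, and a Grade 3-4 listing with all results, are planned. Randomization criterion 7 excludes ongoing laboratory abnormalities of concern to the investigator. No formal testing is planned. These outputs help a reader of the listings but do not correct the EAIR table, and criterion 7 rests on the investigator's judgement, not on grade.

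Two further inferences do not hold. The SAP does not contradict the protocol: Protocol 8.6.3 also uses a value-based definition and is silent on the switch from SEL to placebo. And one abnormality is not counted repeatedly; it enters each exposure column at most once. In 7.2.3 the pre-SEL Baseline plays no part; only the missing newness condition applies there.

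**Conclusion.** The point holds. On the SAP text, an abnormality that emerged on run-in SEL and persists past Study Day 31 enters both the SEL and the placebo counts, in contrast to the adverse-event rule. This raises the placebo rate and attenuates a SEL laboratory signal that does not resolve within the 30-day lag.

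The size cannot be derived from the documents, which give no onset or persistence rates by test. Under the assumed ranges, about 8-16% of the placebo count is carry-over with no SEL effect, and roughly 13-30% if SEL triples onset and the effect persists off drug. The upper figures need both conditions. The direction of the overall ratio also depends on the SEL person-time mismatch, which partly offsets the carry-over today, so the two should be corrected together. The issue concerns descriptive safety tables and does not touch the efficacy analysis.

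**What to change.** In SAP 7.2.2.1, 7.2.2.2 and 7.2.3:

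1. Under placebo exposure, count a value only if it meets the existing grade-increase or liver-threshold criterion **and** either (a) exceeds the grade, or threshold category, of that subject's last value before Study Day 31, or (b) follows an intervening return to the Baseline grade (below threshold for 7.2.3). Condition (b) is needed: with (a) alone, an abnormality that resolves on placebo and recurs at the same grade would be lost.
2. Show carried-over abnormalities in a separate row, so that nothing disappears from view.
3. For these laboratory EAIRs, match person-time to the counting windows: first run-in SEL dose to last SEL dose + 30 days for SEL, and Day 31 to last placebo dose + 30 days for placebo. Without this, the newness rule moves the no-effect ratio to about 1.12-1.24; with it, to about 1.01-1.12. A small tilt remains and should be noted beside the table.

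The cost is a few lines of SAP text and some programming on data already collected. Laboratory denominators would differ slightly from the adverse-event ones unless the same person-time change is made there.
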